07 May 2020	Amendment 1	
 • Added a higher dose of CSL346 in CSL346 treatment arm and updated dose rationale • Updated randomization scheme • Updated statistical analyses of primary and secondary endpoints and added further exploratory analyses • Increased dose volumes and infusion durations • Added dose level stopping criteria • Added injection site reaction as an adverse event of special interest • Provided guidance for administration and dose adjustments for mild injection site reactions • Updated sample size estimation and added allowance for an increase in sample size of up to 124 subjects if there is a higher than expected drop-out rate • Added and revised further exploratory pharmacodynamic biomarkers • Added immunosuppressants as a prohibited concomitant therapy • Revised lifestyle restrictions (described contraceptive barrier method and adjusted alcohol limits) • Made editorial revisions, where applicable
27 May 2021	Amendment 2	
 • Added potential inclusion of subjects with estimated glomerular filtration rate between > 20 and < 45 mL/min/1.73m² subject to endorsement by the Independent Data Monitoring Committee • Changed the adverse events of special interest criteria for increases in albumin-to-creatinine ratio • Added sensitivity analysis employing multiple imputation for missing data

		
• Added sensitivity analysis to reflect the impact of novel coronavirus 2019• Added clarification for use of antihypertensives• Added Screened Analysis Set• Added Interim Analysis for decision making• Added clarification for women of childbearing potential or males with partners of childbearing potential• Made editorial revisions, where applicable
--	--	--

Clinical Study Protocol Synopsis

Title	A Phase 2a, Double-blind, Randomized, Placebo-controlled, Proof of Concept Study of Vascular Endothelial Growth Factor (VEGF)-B Blockade with the Monoclonal Antibody CSL346 in Subjects with Diabetic Kidney Disease
Study Number	CSL346_2001
Sponsor	CSL Behring LLC
Development Phase	2a
Study Product	CSL346 (vascular endothelial growth factor [VEGF]-B antagonist mAb)
Indication	Diabetic kidney disease (DKD)

Study Summary and Overview This is a prospective, multicenter, randomized, double-blind, placebo-controlled, proof of concept study to investigate the efficacy, safety, tolerability, and pharmacokinetics (PK) of repeat doses of CSL346 in 100 subjects with DKD and albuminuria receiving standard of care treatment. The study will be divided into 4 periods: Screening, Lead-in, Treatment, and Follow-up, as shown in the following schematic:

Screening Period

The Screening Period begins with the completion of the informed consent process and includes up to 6 weeks for determination of subject eligibility. During Screening (Visit 1 and Visit 2), the Investigator or delegate will assess the subject’s eligibility for the study according to Inclusion / Exclusion Criteria. A subcutaneous (SC) test infusion is to be done at Visit 2 after other subject eligibility criteria have been confirmed.

Lead-in Period

During the Lead-in Period, subjects will have a study visit approximately 1 week before randomization (Visit 3, Day -7 ± 4 days). The subject's eligibility to continue into the Treatment Period will be assessed according to Randomization Criteria.

Treatment Period

The Treatment Period will include 12 weeks of approximately monthly (every 4 weeks) administration of investigational product (IP). Using an interactive response technology system, eligible subjects will be randomized (1:1:2) to receive blinded IP (8 mg/kg CSL346, 16 mg/kg CSL346, or placebo).

Each subject's first dose of IP at Visit 4 (Day 1) will be an intravenous (IV) loading dose of 3 mg/kg CSL346 (subjects randomized to 8 mg/kg CSL346), 6 mg/kg CSL346 (subjects randomized to 16 mg/kg CSL346), or placebo (subjects randomized to placebo). All IV loading doses will be in a total volume of 10 mL and will be infused over the course of approximately 20 minutes. The subject will then be monitored for approximately 2 hours, during which adverse events (AEs) and vital signs will be recorded periodically as described in the Schedule of Assessments. If no clinically relevant AEs are observed during this time, the subject's first SC dose of IP will be administered as an 8 mg/kg, 16 mg/kg, or placebo 20 mL SC infusion over the course of approximately 40 minutes.

Subjects will receive 3 subsequent SC infusions at Visit 7 (Week 4), Visit 8 (Week 8), and Visit 9 (Week 12) for a total of 4 SC doses.

Guidance is provided for adverse events of special interest (AESIs): injection site reactions; increase in serum creatinine (SCr), albuminuria, or blood pressure (BP); and cardiac-related AEs.

Dose and / or administration adjustments are permitted for mild injection site reactions that are deemed unacceptable and would otherwise lead to discontinuation of the IP.

Relevant unblinded data from all subjects participating in the study will be reviewed by the Independent Data Monitoring Committee

(IDMC) during regularly-scheduled safety and PK reviews, as detailed in the IDMC Charter.

Follow-up Period

The Follow-up Period will continue for 12 weeks after the subject's last dose of IP to evaluate changes in safety, efficacy, PK, and pharmacodynamic (PD) parameters after stopping treatment.

Primary Objective	The primary objective of this study is to evaluate the efficacy of CSL346 administered every 4 weeks for 12 weeks (4 doses) in subjects with DKD.
Primary Endpoint	Change in log-transformed urinary albumin-to-creatinine ratio (ACR) from Baseline to Week 16 (Visit 10)
Secondary Objectives	
The secondary objectives of this study are as follows:
 
 1. To evaluate the safety and tolerability of CSL346 administered every 4 weeks for up to 12 weeks (4 doses) in subjects with DKD 2. To evaluate the effect of CSL346 on SCr concentration and eGFR in subjects with DKD 3. To evaluate the effect of CSL346 on BP in subjects with DKD 4. To evaluate the PK of CSL346 in subjects with DKD 5. To evaluate the immunogenicity of CSL346 in subjects with DKD
Secondary Endpoints	
The secondary endpoints of this study are as follows:
 
 1. Treatment-emergent adverse events, including AESIs, from the time of first dose of IP through End of Study (EOS) 2. Observed value and change from Baseline in SCr and eGFR through EOS 3. Observed value and change from Baseline in systolic and diastolic BP through EOS 4. CSL346 serum PK: maximum concentration (C_{max}) after IV loading dose, time to reach C_{max} in serum (T_{max}) after IV loading dose, C_{max} after first SC dose, T_{max} after first SC dose, area under the concentration-time curve in first dosing interval ($AUC_{0-\tau}$), and trough concentration (C_{trough}) after each dose 5. Presence of anti-drug antibodies at Week 4 (Visit 7), Week 8 (Visit 8), and Week 16 (Visit 10)

Exploratory Objectives

The exploratory objectives of this study are as follows:

1. To explore the effect of CSL346 on the following potential PD biomarkers:
 - Biomarkers of lipid metabolism
 - Biomarkers of glycemic control
 - Novel plasma, serum, and urinary biomarkers
2. To measure the concentration of CSL346 in the urine and explore its association with albuminuria
3. To explore the relationship between PD biomarkers and CSL346 PK characteristics
4. To evaluate the frequency of subjects with macroalbuminuria (ACR > 300 mg/g [> 33.9 mg/mmol]) at Baseline regressing to microalbuminuria (ACR ≥ 30 and ≤ 300 mg/g [≥ 3.39 and ≤ 33.9 mg/mmol]) or normoalbuminuria (ACR < 30 mg/g [< 3.39 mg/mmol]), or from microalbuminuria to normoalbuminuria
5. To explore possible dose response for the primary and secondary efficacy and safety endpoints

Exploratory Endpoints

The exploratory endpoints for this study are as follows:

1. Changes from Baseline to each assessment in fasting values for the following PD biomarkers:
 - Biomarkers of lipid metabolism including, but not limited to, circulating total cholesterol, triglycerides, high density lipoproteins, low density lipoproteins, glycerol, non-esterified fatty acids, and ketones
 - Biomarkers of glycemic control including, but not limited to, fasting glucose and hemoglobin A1c (HbA1c)
 - Novel biomarkers including, but not limited to, serum-free VEGF-B and soluble tumor necrosis factor receptor-1 and urinary VEGF-A, soluble VEGF receptor 1(VEGF-R1), kidney injury molecule -1, neutrophil gelatinase-associated lipocalin, clusterin, and monocyte chemoattractant protein-1 (MCP-1)
 2. Concentration of CSL346 found in urine at Week 1 (Visit 5) and Week 12 (Visit 9)
 3. Number (percent) of subjects who regress from macroalbuminuria to microalbuminuria or normoalbuminuria, or from microalbuminuria to normoalbuminuria at Week 16 (Visit 10) compared to Baseline
-

Study Duration The duration of the study for an individual subject is expected to be up to approximately 34 weeks. This estimate is based on the following:

- An up to 6-week Screening Period
- An up to 4-week Lead-in Period
- A 12-week Treatment Period
- A 12-week Follow-up Period

The overall study duration (ie, first subject's Screening Visit to last subject's EOS Visit) will be approximately 22 months.

Number of Subjects The study will randomize a target of 100 subjects:

- 25 subjects randomized to the 8 mg/kg CSL346 group
- 25 subjects randomized to the 16 mg/kg CSL346 group
- 50 subjects randomized to the placebo group

A subject is considered enrolled in the study once they have signed the informed consent form. A subject is considered eligible for randomization into the study when all inclusion criteria have been met, none of the exclusion criteria have been met, and the randomization criteria have been met.

The actual early discontinuation rate will be assessed throughout the study and up to 124 subjects may be randomized, if necessary, to target 94 completed subjects (subjects who received all doses and completed the Week 16 ACR assessment).

Study Population and Main Criteria for Eligibility *Inclusion*

The study will enroll male and female subjects ≥ 25 years of age with a diagnosis of type 2 diabetes mellitus. Subjects must have a urinary ACR ≥ 150 mg/g (16.95 mg/mmol) from a 24-hour timed urine collection. The initial study population must have eGFR ≥ 60 mL/min/1.73m² and glycosylated HbA1c $< 12\%$.

After an IDMC review of safety and PK data from the first 18 subjects with eGFR ≥ 60 mL/min/1.73m², inclusion of subjects with eGFR ≥ 45 mL/min/1.73m² (including chronic kidney disease stage 3A) will be permitted if approved by the IDMC. Subsequently, after an IDMC review of safety and PK data from the first 36 subjects (at least 8 subjects with eGFR ≥ 45 to < 60 mL/min/1.73m²) followed for at least 4 weeks, inclusion of subjects with eGFR > 20

to $< 45 \text{ mL/min/1.73m}^2$ will be permitted if approved by the IDMC. If inclusion of subjects with eGFR below $60 \text{ mL/min/1.73m}^2$ is endorsed by the IDMC, the following target sample size(s) will be established for subjects with eGFR in the specified range:

- At least 36 subjects with eGFR $< 60 \text{ mL/min/1.73m}^2$
- At least 18 subjects with eGFR $< 45 \text{ mL/min/1.73m}^2$

To achieve these targeted minimums, a restriction may be imposed on the enrollment of subjects with eGFR $\geq 60 \text{ mL/min/1.73m}^2$ and / or $\geq 45 \text{ mL/min/1.73m}^2$.

Subjects must have been taking stable doses of an angiotensin-converting enzyme inhibitor or angiotensin II receptor blocker therapy for at least 8 weeks before Screening. Subjects taking antihypertensive medication(s) must have been taking stable doses for at least 8 weeks before Screening. Every effort will be made to ensure that at least 50% of randomized subjects are receiving concomitant treatment with a sodium-glucose cotransporter 2 inhibitor (dose stable for at least 4 weeks before Screening).

Exclusion

Subjects must not have a current diagnosis of type 1 diabetes mellitus, history of acute kidney injury or chronic dialysis/renal transplant, anticipated renal transplant, uncontrolled hypertension or Class III / IV heart failure, left ventricular ejection fraction $< 50\%$ by echocardiogram, troponin-I $>$ the upper reference limit, b-type natriuretic peptide (BNP) $> 200 \text{ pg/mL}$, or alanine transaminase $> 2x$ the upper limit of normal.

Study Product Dose, Dosing Regimen, and Administration

CSL346 is supplied as a sterile solution for IV and SC infusion at a concentration of 100 mg/mL .

All CSL346 doses will be calculated based on weight and normalized to a standard volume with sterile normal saline. CSL346 will be administered at an initial loading dose of 3 mg/kg or 6 mg/kg IV in the arm, followed by 8 mg/kg or 16 mg/kg SC, respectively, in the abdomen at least 2 hours but no more than 6 hours later. Subsequent SC infusions (8 mg/kg or 16 mg/kg per dose) will be administered every 4 weeks for 12 weeks.

Comparator Product, Dose, Dosing Regimen, and Administration	Placebo consists of normal saline for IV and SC infusion. Dosing administration, regimen, and volume will be matched to CSL346.
Efficacy Assessments	The efficacy of CSL346 will be assessed based on changes in ACR associated with CSL346 treatment. To minimize intrasubject variability, baseline values for these parameters will be based on the geometric mean values from 3 first morning void (FMV) urine collections on 2 separate occasions (ie, 6 total FMV samples) before the first dose of IP. On-treatment assessments of ACR will be the geometric mean values from multiple FMV collections at each time point. Only 2 FMV samples will be collected at Visit 9 because a timed 24-hour sample will also be collected at this Visit. The Follow-up assessment of ACR performed for the primary analysis 4 weeks after the last dose of IP (Visit 10) will be based on the geometric mean of 3 FMV samples. For the EOS Visit, the assessment of ACR will also be based on the geometric mean of 3 FMV samples.
Safety Assessments	The safety and tolerability of CSL346 will be based on the following: 
 • AEs (including AESIs) • Vital signs • Physical examinations • 12-lead electrocardiograms • Clinical laboratory assessments (urinalysis, hematology, biochemistry, troponin-I, BNP, SCr, and eGFR)
Pharmacokinetics	Serial blood samples for the determination of CSL346 concentration will be collected at Visit 4 (Day 1). Single PK samples will also be collected at all subsequent visits (before treatment on SC dosing days).
Exploratory Assessments	Biomarkers of Lipid Metabolism Fasting blood samples for the determination of serum glycerol, non-esterified fatty acids, and ketones will be collected at Visit 3 (Day -7), Visit 4 (Day 1), Visit 7 (Week 4), Visit 8 (Week 8), and Visit 10 (Week 16). Fasting blood samples for the determination of total cholesterol, triglycerides, high density lipoprotein, and low density lipoprotein levels will also be collected at Visit 3 (Day -7), Visit 4 (Day 1), Visit 7 (Week 4), Visit 8 (Week 8), and Visit 10

(Week 16) as part of the standard biochemistry panel.

Biomarkers of Glycemic Control

Blood samples for the determination of HbA1c levels will be collected at Screening (Visit 1), Visit 4 (Day 1), Visit 10 (Week 16) and EOS. Blood samples for the determination of fasting glucose levels will be collected at Visit 3 (Day -7), Visit 4 (Day 1), Visit 7 (Week 4), Visit 8 (Week 8), and Visit 10 (Week 16) as part of the standard biochemistry panel.

Novel Plasma, Serum, and Urinary Biomarkers

Fasting blood samples for the determination of serum free VEGF-B and soluble tumor necrosis factor receptor-1 levels will be collected at Visit 3 (Day -7), Visit 4 (Day 1), Visit 7 (Week 4), Visit 8 (Week 8), and Visit 10 (Week 16).

Urine samples for the determination of VEGF-A, soluble VEGF-R1, kidney injury molecule-1, neutrophil gelatinase-associated lipocalin, clusterin, and monocyte chemoattractant protein-1 will be collected at Visit 3 (Day -7), Visit 4 (Day 1), Visit 7 (Week 4), Visit 8 (Week 8), and Visit 10 (Week 16).

CSL346 in Urine (PK)

Timed 24-hour urine samples for the determination of CSL346 concentration will be collected at Screening (Visit 1, Baseline), Visit 5 (Week 1), and Visit 9 (Week 12).

ACR

As an exploratory assessment, the data generated for the primary analysis will also be used to evaluate changes in clinical characterization of albuminuria: normoalbuminuria, microalbuminuria, or macroalbuminuria.

To do this, each subject's level of urinary ACR (average of available FMV samples at each time point) will be categorized at Baseline and at Visit 10 (Week 16) as:

- Macroalbuminuria (ACR > 300 mg/g [> 33.9 mg/mmol])
- Microalbuminuria (ACR ≥ 30 and ≤ 300 mg/g [≥ 3.39 and ≤ 33.9 mg/mmol]), or
- Normoalbuminuria (ACR < 30 mg/g [< 3.39 mg/mmol])

Transitions between these categories will be described.

**Statistical
Analyses***Sample Size*

The planned sample size is 100 subjects with 50 subjects receiving CSL346 (8 mg/kg, n = 25 and 16 mg/kg, n = 25) and 50 subjects receiving placebo. Assuming an SD of 0.65 for the change from Baseline to Week 16 (Visit 10) in ACR following natural log transformation, a sample size of 94 subjects is estimated to provide 85% power to detect a 27% reduction in the geometric mean ACR for CSL346 versus placebo, ie, $\ln(1 \text{ to } 0.27) = -0.315$ on the natural log scale, using a one-sided alpha = 0.10. The total sample size accounts for an assumed 6% drop-out rate. The actual early discontinuation rate will be assessed throughout the study and up to 124 subjects may be randomized, if necessary, to target 94 completed subjects (subjects who received all doses and completed the Week 16 ACR assessment).

Primary Endpoint Analysis

The primary analysis is a mixed effects model, repeated measures (MMRM) analysis of the change from Baseline through 24 weeks of log ACR, with the primary treatment comparison at Week 16 (Visit 10). The primary comparison of interest is a contrast of 0.5 (8 mg/kg CSL346 + 16 mg/kg CSL346) – Placebo.

For decision-making and development purposes, an interim analysis of unblinded data will be performed after enrollment is complete and all randomized subjects complete the 16-week ACR measurement (ie, 4 weeks after the fourth dose). These results will be summarized in an interim, nonregulatory, analytical report. A final statistical analysis of all efficacy and safety data will occur after all subjects have completed the full 24 weeks of the study for the clinical study report.

Secondary Endpoint Analyses

Treatment-emergent AEs, defined as AEs occurring at or after the start of study treatment, will be summarized for each CSL346 dose level (8 mg/kg and 16 mg/kg) and placebo. An overview summary of AEs, including the number of subjects with any AE; AEs related to study treatment; AEs leading to discontinuation of study treatment; serious adverse events; and deaths will be produced.

Treatment-emergent AEs will be summarized by preferred term and

system organ class as well as severity. AESIs will also be summarized separately.

The analysis of SCr, eGFR, and BP will employ a model similar to the primary endpoint. The analysis for these continuous endpoints is an MMRM analysis of change from Baseline to each post-baseline measurement.

Serum concentration of CSL346 will be listed by individual subject and will be summarized by dose level and nominal time point using descriptive statistics (ie, n, arithmetic mean, SD, coefficient of variation [CV%], median, geometric mean, geometric CV%, minimum, and maximum). Individual subject CSL346 serum concentration versus time will be plotted on linear and semi-logarithmic scales. The C_{trough} of CSL346 will also be summarized visually, by dose level.

The number of subjects with a positive immunogenicity test at any time post-treatment will be counted and compared between treatments with Fisher's Exact Test. The comparison will be of CSL346 (8 mg/kg and 16 mg/kg pooled) versus placebo.

Exploratory Endpoint Analyses

Exploratory endpoints will employ a model similar to the primary endpoint and continuous secondary endpoints. The analysis for these continuous endpoints is an MMRM analysis of change from Baseline to each post-baseline measurement. Exploratory urinary biomarkers will be normalized to creatinine level for analysis and reporting. The number of subjects who regress from macroalbuminuria to microalbuminuria or normoalbuminuria, or from microalbuminuria to normoalbuminuria at Week 16 will be counted and compared between treatments using Fisher's Exact Test. The comparison will be of CSL346 (8 mg/kg and 16 mg/kg pooled) versus placebo.

Data from the exploratory biomarkers will be summarized descriptively by treatment and visit for the PD Analysis Set.

Pharmacokinetic and PD endpoints will be explored graphically to evaluate potential relationships.

Schedule of Assessments

Study Period	Screening		Lead-in	Treatment						Follow-up	
	1	2		3	4	5	6	7	8	9	10
Week	Up to -6 weeks		-1	NA	1	2	4	8	12	16	24
Study Day	≤ 63 days ^A before Day 1	-21	-7	1	8	15	29	57	85	113	169
Visit Window (Days)	NA	± 7	± 4	NA	± 3	± 3	± 3	± 5	± 5	± 7	± 7
Informed consent / IRT registration	X										
Eligibility criteria	X	X									
Randomization criteria ^B			X	X							
Medical history	X										
Demographics	X										
Virology testing	X										
Pregnancy test (FCBP) ^C	X		X	X			X	X	X	X	X
Physical examination ^D		X	X	X	X	X	X	X	X	X	X
Vital signs ^E	X	X	X	X	X	X	X	X	X	X	X
Height and weight ^F	X		X	X	X	X	X	X	X	X	X
12-lead electrocardiogram ^G	X		X	X	X	X	X	X	X	X	X
Echocardiogram ^H	X										
Troponin-I and BNP	X		X	X	X	X	X	X	X	X	X
Coagulation (PT / INR and aPTT)	X										
HbA1c	X			X						X	X
Hematology and biochemistry	X	X ^I	X	X	X	X	X	X	X	X	X
Urinalysis	X			X							
Timed 24-hour urine ^J	X				X				X		
First morning void urine ^K			x3	x3		x3	x3	x3	x2	x3	x3
Morning midstream urine ^L			X	X			X	X		X	
SC normal saline test infusion		X									

Study Period	Screening		Lead-in	Treatment						Follow-up	
	1	2		3	4	5	6	7	8	9	10
Week	Up to –6 weeks		–1	NA	1	2	4	8	12	16	24
Study Day	≤ 63 days ^A before Day 1	–21	–7	1	8	15	29	57	85	113	169
Visit Window (Days)	NA	± 7	± 4	NA	± 3	± 3	± 3	± 5	± 5	± 7	± 7
Randomization				X							
IRT IP assignment				X			X	X	X		
IP administration ^M				IV and SC			SC	SC	SC		
Serum PK sampling ^N				X	X	X	X	X	X	X	X
Local tolerability assessment				X	X	X	X	X	X	X	
Adverse events	From ICF Signature through Last Visit										
Concomitant medications	From ICF Signature through Last Visit										
Immunogenicity				X			X	X		X	
Biomarker sample (blood) ^O			X	X			X	X		X	

ACR = albumin-to-creatinine ratio; aPTT = activated partial thromboplastin time; BNP = b-type natriuretic peptide; BP = blood pressure; EOS = End of Study; FCBP = female subjects of childbearing potential; HbA1c = hemoglobin A1c; ICF = informed consent form; IMP = investigational medicinal product; INR = international normalized ratio; IP = investigational product; IRT = interactive response technology; IV = intravenous; NA = not applicable; PK = pharmacokinetic; SC = subcutaneous; PT = prothrombin time.

Notes to the Schedule of Assessments:

- A:** Screening Visit 1 should be performed within 6 weeks before Screening Visit 2.
- B:** Randomization criteria will include evaluations of BP, serum creatinine, and troponin (see [Section 4.1.3](#) for detailed guidance).
- C:** A serum pregnancy test will be performed at Screening for FCBP; serum or urine pregnancy tests will be performed at all other indicated visits.
- D:** A comprehensive physical examination will be performed at Visit 2 (Day –21) and at EOS. An abbreviated physical examination will be performed for all other indicated visits.
- E:** Vital signs include BP (systolic and diastolic), body temperature, and pulse rate. Blood pressure measurements should be taken in triplicate before all other assessments. Vital signs in general will be collected before any blood samples that are collected at the same time point. At Visit 2 (Day –21), BP will be the only vital sign collected. Instructions for measuring BP will be provided in the Manual of Operations. At Visit 4 (Day 1), vital sign measurements will be taken predose, at 30, 60, and 120 minutes (± 15 minutes) after the first IV dose of IP (before the first SC dose of IP) is administered, then at 30 and 60 minutes (± 15 minutes) after SC dosing.
- F:** Height will be measured at Screening only.

- G:** Electrocardiograms must be performed in triplicate before any blood samples that are collected at the same time point.
- H:** A local assessment of echocardiogram will be performed during Screening unless an echocardiogram was performed for non-study-related reasons within 3 months before Screening.
- I:** At Visit 2 (Day -21), a blood sample will be collected for determination of serum creatinine only.
- J:** A timed 24-hour urine sample will be collected to assess eligibility (ACR) at Screening (Baseline), and to measure CSL346 levels in urine at subsequent indicated visits.
- K:** Subjects will collect urine from their first morning void on 3 consecutive days (2 consecutive days for Visit 9) leading up to and including the morning of each indicated visit.
- L:** Morning midstream urine samples will be collected to evaluate exploratory biomarkers and will also be stored for future research analyses.
- M:** Specific instructions for administration of IP are provided in the IMP Handling Manual. At Visit 4 (Day 1), an initial loading dose of IP will be administered by IV, followed at least 2 hours (but no more than 6 hours) later by the subject's normal prescribed dose by SC infusion. Subsequent doses of IP will be administered by SC infusion.
- N:** Serial blood samples for PK will be collected at Visit 4 (Day 1) predose, at 30 (\pm 5 minutes), 60 (\pm 10 minutes), and 120 (\pm 10 minutes) minutes after the first IV dose of IP (before the first SC dose of IP) is administered, then after the final vital signs measurement. Single PK samples will also be collected at all subsequent visits (before treatment on SC dosing days).

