8.3.2 Urine Samples

Timed 24-hour urine samples are collected for determination of ACR during Screening and for detection of CSL346 in urine at other indicated time points. The subject should collect all urine over a 24-hour period and record start and stop time of the collection period.

FMV urine samples are collected for determination of ACR after Screening. The subject's complete FMV should be collected on 3 consecutive mornings, with the third collection on the morning of the indicated visit. For Week 12, a FMV sample should be collected on 2 consecutive mornings, followed by a 24-hour timed sample, as indicated in Table 9.

Sample collection containers should be kept refrigerated by the subject until brought to the study site.

Midstream urine samples for PD analyses will be collected during regularly scheduled study visits as indicated in the [Schedule of Assessments](#) and in Table 9.

Table 9 Overview of Urine Collections

Visit	Urine Samples Required	Collection Day(s)
Screening (Visit 1)	Timed 24-hour collection	Within 1 week of Visit 1
Screening (Visit 2)	None	--
Week -1 (Day -7 / Visit 3)	FMV x3 Midstream	Day -9, Day -8, Day -7 Day -7 during visit
Day 1 (Visit 4)	FMV x3 Midstream	Day -2, Day -1, Day 1 Day 1 during visit
Day 8 (Visit 5)	Timed 24-hour collection	Morning of Day 7 through morning of Day 8
Week 2 (Day 15 / Visit 6)	FMV x3	Day 13, Day 14, Day 15
Week 4 (Day 29 / Visit 7)	FMV x3 Mid-stream	Day 27, Day 28, Day 29 Day 29 during visit
Week 8 (Day 57 / Visit 8)	FMV x3 Midstream	Day 55, Day 56, Day 57 Day 57 during visit
Week 12 (Day 85 / Visit 9)	FMV x2 Timed 24-hour collection	Day 83, Day 84 Morning of Day 84 through morning of Day 85
Week 16 (Day 113 / Visit 10)	FMV x3 Midstream	Day 111, Day 112, Day 113 Day 113; during visit
Week 24 (Day 169 / EOS)	FMV x3	Day 167, Day 168, Day 169

EOS = End of Study; FMV = first morning void.

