8.6.4.5.2 Administration of IP and After

The following additional procedures are to be conducted and documented at Visit 8 as related to administration of IP:

- IRT IP assignment
- Administer the third SC dose of IP
- Collect information on AEs, including local tolerability assessment
- Remind subject to collect FMV samples on Day 83 and Day 84, to collect a 24-hour urine sample beginning on the morning of Day 84 and continuing until the morning of Day 85

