8.6.4.6 Treatment Visit 9 (Week 12, Day 85)

8.6.4.6.1 Before Administration of IP

The following procedures are to be conducted and documented at Visit 9 before administration of IP:

- Perform serum or urine pregnancy test (FCBP only)
- Perform abbreviated physical examination
- Measure vital signs (BP in triplicate)
- Measure weight
- Perform 12-lead ECG (triplicate)
- Collect blood samples for the following:
 - Standard hematology and biochemistry testing
 - Troponin-I and BNP
 - Biomarker analysis

- Collect trough PK blood sample
- Collect urine samples for the following:
 - FMV (for Days 83 and 84)
 - Timed 24-hour urine sample (for Day 84 to 85)
- Collect information on AEs, including local tolerability assessment
- Collect information on concomitant therapies

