## 16.7 Factors to be Addressed in Per Protocol Analysis Set

The following define major events which could result in subjects' data being removed from the per protocol analysis set. Subjects' data may be removed completely or from the time of the major event up to the end of subject's study participation.

At a specific time point, ACR measurements are to be used in summaries and analysis as long as there are at least 2 FMVs for that time point (4 FMVs for baseline) available.

- Extrinsic factors with the potential to impact ACR during treatment period. For any such occurrences, data points at or beyond the date of the occurrence will be excluded from analysis. [These data will be provided by CSL.]
  - Protocol deviations:
    - Subjects with substantial change in blood pressure medications or DKD medications;
    - Prohibited concomitant medications;
    - Initiation of lipid lowering agent;
    - Change in SGLT2i doses;
    - Change in dose in agents that impact tubular secretion of serum creatinine (fibrates).
    - Missed intermittent dose
  - Cardiac AESI with heart failure.
- Study drug [to be derived by Parexel]:
  - For subjects receiving fewer than 4 doses of the investigational product, all data on or after the date of the last dose + 4 weeks + 1 day will be excluded. If no dose is administered then all data for that subject will be excluded.
- Violation of study entry criteria. In these cases, all data from these subjects will be excluded from analysis. [These data will be provided by CSL.]
  - Baseline Glycosylated HbA1c  $\geq 12\%$ ;
  - Change in SCr from Visit 1 (<63 Days before Day 1) to Visit 2 (Day -21)  $> 0.3$  mg/dL (26.5  $\mu\text{mol/L}$ );
  - Uncontrolled hypertension: SBP  $> 160$  mmHg or DBP  $> 100$  mmHg prestudy (SBP $>150$  mmHg at randomization).

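### Schedule note K puts the two Visit 9 first morning voids on Days 84 and 85; Table 9 and the visit procedures put them on Days 83 and 84, ahead of the 24-hour urine. The note should be corrected in both documents (minor).

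*Protocol*

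**What the plan says.** Visit 9 (Week 12, nominally Day 85) is the only visit with both FMV samples for ACR and a timed 24-hour urine for CSL346. The instructions on collection days fall into two groups.

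- **Schedule of Assessments, note K (protocol, repeated in SAP 16.8).** FMVs are collected on consecutive days, with Visit 9 singled out: "2 consecutive days for Visit 9) leading up to and including the morning of each indicated visit".
- **Protocol 8.3.2.** For Week 12, "a FMV sample should be collected on 2 consecutive mornings, followed by a 24-hour timed sample".
- **Protocol Table 9.** The Week 12 entry for the two collections reads "Day 83, Day 84 Morning of Day 84 through morning of Day 85".
- **Protocol 8.6.4.5.2 (Visit 8).** The instruction to site staff is "Remind subject to collect FMV samples on Day 83 and Day 84", followed by the 24-hour collection from the morning of Day 84.
- **Protocol 8.6.4.6.1 (Visit 9).** The procedure list names the same FMV days and a "Timed 24-hour urine sample (for Day 84 to 85").

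Two further provisions bear on the consequence. For the 24-hour sample, 8.3.2 states: "The subject should collect all urine over a 24-hour period and record start and stop time of the collection period". SAP 16.7, on the Per-Protocol set, allows an ACR time point to be used "as long as there are at least 2 FMVs for that time point (4 FMVs for baseline) available".

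**The concern.** Note K and the detailed instructions cannot both be right for Visit 9. Note K is also operative text. Protocol 8.1.3 refers to the Schedule for the timing of FMV samples, 8.1 does so for clinical procedures generally, and 3.1 says study procedures are conducted as the Schedule describes. Neither document says which text prevails if they differ.

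A site that works from note K takes its second FMV on the morning of Day 85, when the 24-hour collection is due to end. That void may then be wanted twice, as a complete FMV and as part of a collection that is meant to hold all urine. Two outcomes are possible:

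- The void goes to the FMV container. The Week 12 24-hour urine is then incomplete. It is one of two post-dose time points for the exploratory urine CSL346 endpoint, and it feeds the Day 85 urine CSL346 plots in SAP section 14.
- The void stays in the 24-hour container. Only the Day 84 FMV remains for Week 12 ACR.

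**Working it through.** **Step 1. Apply note K to every FMV visit and compare with Table 9.** The rule is three consecutive mornings (two at Visit 9) ending on the visit morning, with no Day 0. Nominal visit days come from the Schedule.

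| Visit | Visit day | Note K gives | Table 9 gives |
|---|---|---|---|
| 3 | -7 | -9, -8, -7 | -9, -8, -7 |
| 4 | 1 | -2, -1, 1 | -2, -1, 1 |
| 6 | 15 | 13, 14, 15 | 13, 14, 15 |
| 7 | 29 | 27, 28, 29 | 27, 28, 29 |
| 8 | 57 | 55, 56, 57 | 55, 56, 57 |
| **9** | **85** | **84, 85** | **83, 84** |
| 10 | 113 | 111, 112, 113 | 111, 112, 113 |
| End of study | 169 | 167, 168, 169 | 167, 168, 169 |

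Note K reproduces Table 9 at seven of eight visits. It fails only at Visit 9, the visit for which it makes an explicit exception. The exception changes the number of mornings from three to two but leaves the end day on the visit morning.

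**Step 2. Check the overlap.** The 24-hour collection runs from the Day 84 morning to the Day 85 morning.

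- Under Table 9 the FMVs fall on Days 83 and 84 and the 24-hour collection follows them. No void is needed for both.
- Under note K the second FMV falls on the Day 85 morning, at the end of the 24-hour window.

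**Step 3. Consequence for Week 12 ACR if one FMV is lost.** The input is the within-subject CV of about 30% for FMV ACR in protocol 9.1.3.3. Voids are assumed independent.

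- Log-scale variance of one FMV: ln(1 + 0.30²) = ln(1.09) = 0.0862, SD 0.294.
- Geometric mean of two FMVs: 0.0862 / 2 = 0.0431, SD 0.208.
- One FMV only: 0.0862, SD 0.294.

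The sampling variance doubles. For scale, the planning SD of 0.65 gives a variance of 0.65² = 0.4225. That SD is stated for the Week 16 change and is borrowed here only for comparison. Adding the extra 0.0431 gives 0.4656, an SD of about 0.68 for an affected subject's Week 12 value, or about 10% more variance (0.0431 / 0.4225).

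**Step 4. Handling under the SAP.**

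- ITT (SAP 10.1.2): the available values are averaged, so the single void is used.
- Per-Protocol (SAP 16.7): fewer than two FMVs are available, so that subject's Week 12 ACR is not used. The Per-Protocol set carries both sensitivity analyses of the primary endpoint in SAP 10.1.3.
- Week 16 (Visit 10): three FMVs on Days 111 to 113 under either text.

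**The case against.** The strongest reply is that the design is sound and only a footnote is loose. Table 9, the Visit 8 reminder and the Visit 9 procedure list all name Days 83 and 84, and 8.3.2 puts the FMVs ahead of the 24-hour collection. Protocol 8.1.3 explains that Visit 9 has two FMVs because of the 24-hour sample. Subjects are to be reminded of named days, so an overlap needs a site to follow the footnote against three more specific instructions. This stands, and it limits the point to sites that do so.

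A second reply is that the overlap need not damage a sample. Urine handling details are left to a laboratory manual that is not among the documents, and it may allow a void to be sampled for ACR and then added to the 24-hour container. This stands in part. Protocol 8.3.2 asks for the complete FMV and for all urine over the 24 hours and describes no splitting, but loss of a sample is a risk and not a certainty.

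A third reply is that Week 12 is a supporting visit and urine CSL346 is exploratory. This also stands and sets the severity.

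None of these removes the contradiction. Note K is text that the protocol tells sites to use, and at Visit 9 it gives different days from every detailed instruction.

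**Conclusion.** Note K is inconsistent with protocol 8.3.2, Table 9, 8.6.4.5.2 and 8.6.4.6.1 at Visit 9, in both documents. Severity is minor.

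Where note K is followed, that subject may have either an incomplete Week 12 urine CSL346 sample or a single Week 12 FMV. In the second case Week 12 ACR leaves the Per-Protocol set, and the ITT value has a log-scale sampling variance of about 0.086 instead of 0.043. Those figures rest on the protocol's 30% CV and on independent voids. The documents do not show how many subjects would be affected.

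Two stronger readings are not supported:

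- A reader might infer that one of the two Week 12 samples is spoiled by design. It is not: Table 9 and the visit procedures avoid the overlap, and sites that follow them collect correctly.
- A reader might infer a bias of known size or direction in Week 12 urine CSL346. The documents give neither the share of 24-hour volume in the first void nor its relative CSL346 concentration. Losing that void would lower the measured concentration if it is more concentrated than the rest and raise it if less. Excreted amount is not among the planned analyses.

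The Week 16 primary comparison is not directly affected.

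**What to change.** In note K of the protocol Schedule and of SAP 16.8, state that for Visit 9 the two FMVs are collected on the two mornings before the visit morning (nominally Days 83 and 84), before the 24-hour collection starts, as in Table 9. Wording relative to the visit morning is preferable to fixed days alone, because Visit 9 has a window of ±5 days.

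The sentence should only bring note K into line with Table 9. It should not add a rule on how the Day 85 void is handled, since neither document states one and the laboratory manual may cover it.

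The cost is one sentence in each document, with no extra sample or visit and no change to any analysis.
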